2.1 Primary Objective

To assess the efficacy of ECM products in promoting constructive healing as determined by the ability of the resection site to lift during follow-up

2.2 Secondary Objective

To assess the efficacy of ECM products in promoting constructive healing as determined by endoscopic inspection via white light and electron chromoendoscopy.

[figure not shown]
3 Study Design

3.1 General Design

This is a randomized study on the efficacy of ECM in promoting constructive healing following endoscopic resection (EMR). 20 patients anticipated to undergo endoscopic resection will be recruited in the outpatient setting from the Barrett's Esophagus Unit. Prior to endoscopy, patients will complete a standardized questionnaire (Mayo Dysphagia Questionnaire) and the physician will use the Mellow-Pinkas scale to assess baseline dysphagia. Patients with lesions that lift and are amenable to cap-assisted EMR will be randomized to receive ECM to the defect site vs. standard of care. All patients should be on standard of care double dose proton-pump inhibitor therapy (Omeprazole 40mg PO daily or the equivalent); if this has not been initiated they will be provided a prescription .

In both groups, patients will be brought back for repeat standard of care clinic and endoscopic assessments in 12-16 weeks, or sooner if needed. A clinical dysphagia assessment will be performed with repeat of the above questionnaires. Endoscopy will involve inspection of the wound site, and images in white-light and electron chromoendoscopy will be taken for blinded evaluation later. Submucosal saline injection at the wound site will be performed to determine its ability to lift.

Any patients receiving esophageal dilations will be noted. Patients requiring esophagectomy will be excluded from the primary objective of the study but their surgical specimen at the site of endoscopic resection will be evaluated for evidence of constructive healing.

3.2 Primary Study Endpoints

The primary endpoint will be efficacy of ECM in promoting mucosal lift with fluid injection after healing from prior EMR.

3.3 Secondary Study Endpoints

Secondary endpoints include efficacy of ECM in preventing symptomatic esophageal stricture formation requiring dilation, preventing dysphagia as determined by questionnaires, and mitigating formation of post-resection scarring as determined by blinded comparison of

pre- and post-resection images (taken using white-light endoscopy and electron chromoendoscopy).

3.4 Primary Safety Endpoints

Primary safety endpoints include overall survival, incidence of all serious adverse events including unanticipated adverse device effects, incidence of technical and device failures and malfunctions, and quality of life as measured by the above dysphagia questionnaires.

4 Subject Selection, Enrollment and Withdrawal

Patients will be recruited from the Barrett's Esophagus clinic where patients with Barrett's esophagus, esophageal cancer, and/or esophageal nodules are referred for consideration of endoscopic evaluation and management. Patients with advanced esophageal cancer are typically not referred as they warrant chemoradiotherapy or palliative care, and are not candidates for endoscopic management. Thus, this clinic presents a selective population to screen from, and one we anticipate will be able to provide the proposed number of subjects for this study. It is estimated 75-100 patients with esophageal lesions undergoing EMR will be screened to ultimately meet study enrollment goals.

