4.4 Early Withdrawal of Subjects

4.4.1 When and How to Withdraw Subjects

Subjects will be withdrawn from the study if any adverse events related to EMR, or application of ECM occurs, including major bleeding, perforation, or infection. Patients will also be withdrawn if after EMR the patient proceeds to esophagectomy.

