7.3 Subject Population(s) for Analysis

All-completed population: Only subjects who completed ALL study related procedures and follow-up will be included (Per Protocol) maybe adjusted to subjects who completed the majority of the study visits and procedures. Patients lost to follow-up will be accounted for during calculation of the attrition rate.

8 Safety and Adverse Events

All adverse events occurring during the study, including those not meeting the criteria of an Unanticipated Adverse Device Effect (UADE) will be recorded on the appropriate case report form. Records of these events will be maintained and reports submitted to the FDA and IRB according to the regulatory requirements. Expected clinical adverse events and nonsignificant (not serious) clinical adverse events will not be reported. Expected clinical adverse events and anticipated adverse device effects are those listed in Section 1.5.2.

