8.1 Definitions

Unanticipated Adverse Device Effect (UADE)

A UADE is any serious adverse effect on health or safety or any life-threatening problem or death caused by, or associated with, a device if that effect, problem or death was not previously identified in nature, severity, or degree of incidence in the investigational plan or IDE application (including a supplementary plan or application), or any other unanticipated serious problem associated with a device that relates to the rights, safety, or welfare of subjects.

Adverse Effect (Event)

Any untoward medical occurrence in a subject involved in clinical study of an investigational device; regardless of the causal relationship of the problem with the device or, if applicable, other study related treatment(s).

Associated with the investigational device: There is a reasonable possibility that the adverse effect may have been caused by the investigational device.

Life-threatening adverse effect: Any adverse effect that places the subject, in the view of the investigator, at immediate risk of death from the effect **as it occurred**. It does not include a reaction that, had it occurred in a more severe form, might have caused death.

Serious adverse effect: An adverse effect is considered “serious” if, in the view of the investigator, it results in any of the following outcomes:

- death
- a life-threatening AE
- inpatient hospitalization or prolongation of existing hospitalization
- a persistent or significant disability/incapacity
- a congenital anomaly/birth defect.

Unanticipated adverse effect: Any adverse effect, the nature, specificity, severity, or frequency of which is not consistent with the risk information in the clinical study protocol or elsewhere in the current IDE application.

General Physical Examination Findings

At screening, any clinically significant abnormality should be recorded as a preexisting condition. At the end of the study, any new clinically significant findings/abnormalities that meet the definition of an adverse event must also be recorded and documented as an adverse event.

Hospitalization, Prolonged Hospitalization or Surgery

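### Bleeding, perforation, infection or application injury treated without admission reaches a listed safety endpoint only by investigator judgement or as a device malfunction

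*Combined protocol and SAP*

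**What the plan says.** Section 3.4 names overall survival, the "incidence of all serious adverse events including unanticipated adverse device effects", and the "incidence of technical and device failures and malfunctions, and quality of life as measured by the above dysphagia questionnaires". It names no endpoint for procedural complications as such.

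Section 8.1 calls an adverse effect serious if, "in the view of the investigator, it results in any of the following outcomes": death, a life-threatening event, "inpatient hospitalization or prolongation of existing hospitalization", lasting or significant disability, or "a congenital anomaly/birth defect". Life-threatening is in turn "Any adverse effect that places the subject, in the view of the investigator, at immediate risk of death from the effect" as it occurred. A UADE must also be serious, life-threatening or fatal, and not previously identified in the investigational plan.

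The harms the protocol has in mind are stated elsewhere. Section 1.5.2 gives injury while applying the ECM as a potential risk of the device. Section 4.4.1 says: "Subjects will be withdrawn from the study if any adverse events related to EMR, or application of ECM occurs, including major bleeding, perforation, or infection". Section 7.3 then defines a single analysis population, those who completed all procedures and follow-up, possibly relaxed to those who completed most of them.

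On data, Section 8 and 8.2 require every adverse event to be recorded, and the worksheet in 8.3.1 asks about severity and whether intervention was needed. Section 7.2 plans descriptive statistics for all variables but names no adverse-event table or comparison.

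**The concern.** The event-based safety endpoints pass through one filter, seriousness, and that filter has no entry for an event that needed treatment to avert a worse outcome. Consider a subject whose perforation or bleed is closed during the endoscopy and who is not admitted. Whether that event is counted depends on a judgement that it was immediately life-threatening or disabling, or on its being classed as a device malfunction. The plan does not say that this judgement is made blind to arm, and 5.2 has allocation take place during the procedure.

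The trial is meant to support larger studies of ECM after more extensive resections (1.5.1). A report of no serious events in the ECM arm and a report of one perforation in the ECM arm are different messages to carry into those studies. Under the present endpoint list, the same data could yield either.

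**Working it through.** **1. Trace one event through the definitions.** Take an application injury, major bleed, perforation or infection that is treated without admission and is not fatal.

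| Route into 3.4 | Requirement | Met? |
|---|---|---|
| Overall survival | Death | No |
| SAE: hospitalisation | Inpatient admission or a prolonged stay | No, by construction |
| SAE: life-threatening | Investigator's view of immediate risk of death | Discretionary |
| SAE: disability | Persistent or significant, in the investigator's view | Discretionary |
| SAE: birth defect | Congenital anomaly | Not applicable |
| UADE | Serious, and not previously identified | Fails unless judged serious; harder still because 1.5.2 and 4.4.1 already name these events |
| Device failure or malfunction | A malfunction | Only if one occurred |
| Quality of life | Dysphagia questionnaire score | Not a count of complications |

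The passage in 8.1 that treats events leading to hospitalisation as UADEs does not help, because it too depends on hospitalisation. No route is certain, and the two that are always open rest on judgement.

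**2. Follow the subject into the analysis set.** Section 4.4.1 withdraws the subject for an event related to EMR or to ECM application. Section 7.3 keeps completers and gives no separate safety population. Section 4.4.2 attempts follow-up of withdrawn subjects but does not return them to an analysis set. The affected subject may therefore be missing from the denominator as well as the numerator.

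**3. Arm size.** Section 7.1 states 10 per group for 20% against 80% lift, power 0.8 and alpha 0.05. The two-sided pooled formula without continuity correction is

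n = [z(0.975)·√(2·p̄·(1−p̄)) + z(0.80)·√(p1(1−p1) + p2(1−p2))]² / (p2−p1)², with p̄ = 0.5

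= [1.960 × 0.7071 + 0.8416 × 0.5657]² / 0.36 = (1.3859 + 0.4761)² / 0.36 = 3.467 / 0.36 = 9.63, which rounds up to 10.

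The stated figure is reproduced. It is used here only as the denominator.

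**4. Size of one uncounted event** (exact two-sided 95% intervals).

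- One event in 10 subjects: 1/10 = 10 percentage points.
- Reported as 0/10: upper limit 1 − 0.025^(1/10) = 30.8%.
- Reported as 1/10: lower limit 1 − 0.975^(1/10) = 0.3%; upper limit, the 97.5% quantile of Beta(2, 9), = 44.5%.
- Subject withdrawn and dropped, reported as 0/9: upper limit 1 − 0.025^(1/9) = 33.6%.

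**5. Timing.** Section 5.2 randomises immediately after resection. A bleed or perforation that occurs during resection precedes allocation and cannot be an effect of ECM. A count by arm that mixes the two periods would attribute resection events to an arm.

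**The case against.** A reader might infer that such an event can never enter a safety endpoint. The documents do not support that. An investigator may well judge a perforation or major bleed life-threatening, which needs no admission. A failed fixation could count as a malfunction. The list in 3.4 is also introduced as inclusive, not exhaustive.

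A reader might also infer that the plan loses or suppresses these events, citing the sentence in Section 8: "Expected clinical adverse events and nonsignificant (not serious) clinical adverse events will not be reported". In context that sentence follows one about submissions to the FDA and IRB, so it most naturally governs regulatory reporting and not the trial's own tables. All adverse events are recorded, and the general descriptive statistics in 7.2 could cover them.

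Nor does 4.4.1 show that the protocol ranks bleeding, perforation and infection as specially grave. Withdrawal applies to any related adverse event, and these three are examples.

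Finally, 8.5 stops enrolment at any adverse event, serious or not, so complications could not build up unnoticed through continued recruitment. That limits how many may occur. It does not say how the first one is tabulated, and one is enough to separate 0/10 from 1/10. If enrolment did stop early, the arms would be smaller than 10 and each event would weigh more.

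These replies remove the absolute claim and any claim about data capture. What stands is that no listed endpoint is certain to count the named harms, and that the stated analysis population may exclude the subjects who had them.

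**Conclusion.** The point holds as a defect of endpoint definition and tabulation. Counting a non-admitted bleed, perforation, infection or application injury depends on investigator judgement or on a malfunction classification, and the combination of 4.4.1 with 7.3 may remove the affected subject from the analysis.

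The size is 10 percentage points of an arm per event. The exact intervals are wide and overlap whichever way the event is classified, so the consequence is for what is reported as having happened, not for any test of safety between arms. The conclusion assumes full arms of 10, at least one such event treated without admission, and 7.3 applied to safety as written. The documents give no frequency for such events, and none is claimed here.

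**What to change.** In 3.4, add a safety endpoint: the number and percentage of all randomised subjects in each arm, including those withdrawn under 4.4.1, with major bleeding, perforation, infection or injury during ECM application, regardless of seriousness or hospitalisation. Show events that occurred before randomisation (during resection) separately from those after it. State in 7.3 that this table uses all randomised subjects and not the completers. Give exact confidence intervals, because the arms are small.

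The data are already required by 8.2 and the 8.3.1 worksheet, provided the time of each event relative to randomisation is noted. The cost is a few lines of protocol text and one table, and the stated safety rates may look less favourable. The definition of serious in 8.1 and the regulatory reporting sentence in Section 8 need not change.

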4.1 Inclusion Criteria

- 18 and older
- Male or female
- Able to provide consent
- Scheduled for standard of care endoscopy that may require initial EMR evaluation of esophageal lesions
- Histological evidence of intestinal metaplasia with dysplasia or intramucosal carcinoma

4.2 Exclusion Criteria

- Pregnant women
- Age less than 18
- Prior esophageal EMR or ESD in the same region
- Anyone unable to provide informed consent
- Medical co-morbidities precluding EGD evaluation
- History of chemoradiotherapy to the neck/esophagus
- Unable to stop anticoagulation therapy (non-steroid anti-inflammatory medications are permissible)

4.3 Subject Recruitment, Enrollment and Screening

Subjects will be recruited from the endoscopic practice of the Principal Investigator and Co-Investigator. Patients will undergo screening for inclusion and exclusion criteria at the time of clinical consultation.

4.4 Early Withdrawal of Subjects

4.4.1 When and How to Withdraw Subjects

Subjects will be withdrawn from the study if any adverse events related to EMR, or application of ECM occurs, including major bleeding, perforation, or infection. Patients will also be withdrawn if after EMR the patient proceeds to esophagectomy.

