1.1 Background

The relatively recent introduction of endoscopic resection techniques (endoscopic mucosal resection [EMR] and endoscopic submucosal dissection [ESD]) have enabled endoscopists to excise larger amounts of tissue for accurate staging, and often curative treatment of early esophageal adenocarcinoma. These techniques have largely supplanted esophagectomy for small esophageal cancers which carries significant risks of morbidity and mortality.

One limitation of endoscopic resection, however, is the risk of esophageal stricture formation at the site of resection as a result of the inflammatory healing process that ensues after deep mucosal injury. The esophagus has limited regenerative ability and the default response is volume replacement of the defect with fibrosis.¹ Esophageal stricture can significantly impact a patient's quality of life and often requires treatment via multiple endoscopies for sequential pneumatic dilations, which carry risk of perforation. It has been reported that the risk of stricture formation is directly proportional to the size of the resection defect. Patients with mucosal defects greater than 75% of the esophageal circumference carry a significantly greater risk of stricture formation², and in patients with full circumferential resection the risk may be as high as 88%.^{3,4} Hence, extensive endoscopic resection typically give endoscopists pause. However, this risk of stricture is often justified by the need to excise the lesions en bloc to ensure accurate determination of depth of invasion and also to ensure the complete removal of the lesion.

Various interventions have been described in an effort to prevent stricture formation, including intralesional and systemic steroids, preventative balloon dilation, and prophylactic covered stent, but results are conflicting.⁵ Currently, most endoscopists limit EMR to anticipated defects of 2 cm in diameter or 50% esophageal circumference in an effort to prevent stricture formation.

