4.4.2 Data Collection and Follow-up for Withdrawn Subjects

An attempt will be made to collect follow-up data for withdrawn subjects, as well as patients who undergo esophageal surgery (i.e., surgical histology of the resection site). These patients will be called to collect this data.

5 Study Device

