5.8.4 Return or Destruction of Study Device

We will order clinical supply as needed and dispose of unused supply. We do not anticipate needing to return supplies.

6 Study Procedures

6.1 Visit 1

Patients will be recruited from the Barrett's Esophagus Clinic. Patients referred for endoscopic evaluation of Barrett's esophagus with high grade dysplasia, esophageal nodules or early esophageal cancer and are scheduled for EMR, will be screened using inclusion and exclusion criteria outlined above. Patients meeting inclusion criteria will be consented for study inclusion and will be asked to complete the Mayo Dysphagia Questionnaire.

6.2 Visit 2

Visit 2 refers to the procedure during which the patient will undergo planned EMR of the esophageal lesion. Visits 1&2 may take place on the same date. Patients will undergo endoscopy and those amenable to standard EMR will be randomized to receive ECM or receive standard of care (i.e., observation). ECM will be applied to patients in the manner described above.

6.3 Visit 3

All patients will be scheduled to return in approximately 12-16 weeks (up to 6 months) following EMR for follow-up endoscopic evaluation. Patients will repeat the Mayo Dysphagia Questionnaire prior to endoscopy. During endoscopy, the EMR site will be inspected and multiple pictures will be taken in white-light as well as electron chromoendoscopy (i.e., narrow band imaging). Thereafter, standard submucosal saline injection of the healed EMR site will be performed, and the endoscopist will record whether no lift, a partial lift, or complete lift was observed. Symptomatic structuring will be treated with standard pneumatic dilation.

Schedule of Events			
Study Activity	Baseline*	Procedure*	Follow-up procedure (3-4 months)
Consent	X		
History	X		X
Physical Exam	X	X	X
Disease State Symptom Survey	X		X
Concurrent Medications	X	X	X
Adverse Events		X	X
Serious Adverse Events		X	X

*Baseline and Procedure may be on the same date/visit.

7 Statistical Plan

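### The adverse-event withdrawal rule in 4.4.1 can be read to cover stricture and dysphagia, which 3.3 makes secondary endpoints, so follow-up data may be lost in a way that depends on outcome

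*Combined protocol and SAP*

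**What the plan says.** **The withdrawal rule.** Section 4.4.1: "Subjects will be withdrawn from the study if any adverse events related to EMR, or application of ECM occurs", followed by "including major bleeding, perforation, or infection". Progression to esophagectomy is a separate trigger. Section 4.4.2 promises an attempt to obtain follow-up data on withdrawn subjects: "These patients will be called to collect this data".

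**What counts as an adverse event.** Section 8.1: "Any untoward medical occurrence in a subject involved in clinical study of an investigational device; regardless of the causal relationship". The same section counts a preexisting condition as an adverse event if it worsens during the study. Section 1.1 describes "the risk of esophageal stricture formation at the site of resection as a result of the inflammatory healing process", so the protocol itself links stricture to the resection.

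**How stricture and dysphagia are used.** Section 3.3: "Secondary endpoints include efficacy of ECM in preventing symptomatic esophageal stricture formation requiring dilation, preventing dysphagia as determined by questionnaires". Section 3.1 has dilations noted and, in the same paragraph, excludes only esophagectomy patients from the primary objective. Section 6.3 (Visit 3): "Symptomatic structuring will be treated with standard pneumatic dilation". Sections 1.6 and 3.1 allow symptomatic patients to come back earlier than scheduled.

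**Who is analysed.** Section 7.3 limits the analysis to subjects who completed every procedure and all follow-up, with an undefined option to relax this to those who completed most of them. Section 5.4 names only loss to follow-up and referral for surgery as exclusions from the primary analysis. Section 7.2 expects no missing data and gives no method for handling them.

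**The concern.** A post-EMR stricture is an untoward event that the protocol attributes to the resection, so on its words 4.4.1 reaches it. New dysphagia, or baseline dysphagia that worsens, can be reached in the same way. The same events are what 3.3 sets out to compare between arms.

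A site that applies 4.4.1 literally to a patient with an early stricture would withdraw that patient. The telephone call could recover a reported dilation or questionnaire answers. It could not supply the saline-injection result, the white-light and chromoendoscopy images, or the physician's Mellow-Pinkas score. Poorly healed patients would then be the ones with missing data, and the arm with more strictures would lose more of them. Changing the analysis population later cannot restore measurements that were never taken.

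**Working it through.** **1. The passages side by side**

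| Section | Treatment of a patient with stricture or dysphagia |
|---|---|
| 4.4.1 with 8.1 and 1.1 | Withdrawn, if the event counts as an EMR-related adverse event; no exemption |
| 1.6, 3.1 | Returns early if symptomatic; dilation noted; no withdrawal mentioned |
| 3.3 | Contributes a secondary efficacy outcome |
| 6.3 | Stricture treated at Visit 3; no withdrawal mentioned |
| 7.3 | Dropped from the analysis if procedures are incomplete, unless the rule is relaxed |

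No passage says which of these governs. Section 8 treats expected events separately, but only for reporting, and the section it points to (1.5.2) lists neither stricture nor dysphagia.

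**2. The plan's own figure.** The document gives a sample size for lift only (7.1): 20% vs 80%, power 0.8, alpha 0.05, 10 per group. With the two-sided pooled normal formula,

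n = [1.960·√(2·0.5·0.5) + 0.842·√(0.2·0.8 + 0.8·0.2)]² / 0.6² = (1.386 + 0.476)² / 0.36 = 9.6, rounded up to 10 per arm.

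This reproduces the plan; power at 10 per arm is 0.817. No dropout allowance is stated.

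**3. Stricture comparison (assumed rates).** Let p be the true stricture proportion in an arm and f the share of stricture patients who are withdrawn and then dropped from the analysis. The observed proportion is p(1 − f)/(1 − pf).

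For 30% vs 10% with f = 0.5:
- control 0.15/0.85 = 17.6%
- ECM 0.05/0.95 = 5.3%
- difference 12.4 points, from unrounded values

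| Assumed control vs ECM | f = 0 | f = 0.5 | f = 1 |
|---|---|---|---|
| 10% vs 0% | 10 points | 5.3 | 0 |
| 20% vs 10% | 10 points | 5.8 | 0 |
| 30% vs 10% | 20 points | 12.4 | 0 |
| 50% vs 10% | 40 points | 28.1 | 0 |

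At f = 1 the 30% vs 10% case leaves 0/7 vs 0/9. That column requires three things together: every stricture patient is withdrawn, 7.3 is applied strictly, and strictures already recorded are not counted.

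**4. Lift comparison.** Start from the planned 2/10 vs 8/10 (60 points). Suppose every strictured site is also a non-lifter and all are dropped:

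| Assumed strictures (control, ECM) | Lift, control vs ECM | Difference |
|---|---|---|
| 1, 0 | 2/9 = 22.2% vs 8/10 = 80.0% | 57.8 points |
| 2, 1 | 2/8 = 25.0% vs 8/9 = 88.9% | 63.9 points |
| 3, 1 | 2/7 = 28.6% vs 8/9 = 88.9% | 60.3 points |
| 5, 1 | 2/5 = 40.0% vs 8/9 = 88.9% | 48.9 points |

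The difference moves either way. What is lost reliably is precision. With the planned rates held fixed, approximate power falls from 0.817 at 10 per arm to 0.768 at 9 per arm and 0.703 at 7 vs 9.

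**The case against.** The complications named in 4.4.1 are acute, and the passages that deal with stricture directly keep the patient on study: dilation is noted (3.1) and stricture is treated at Visit 3 (6.3). An early return for symptoms, allowed by 1.6 and 3.1, can itself be the study assessment, with questionnaires, images and saline injection done then. A stricture first found at Visit 3 comes at the last scheduled visit, so little remains to withdraw from. Section 8.2 requires all adverse events to be recorded, so withdrawal does not erase a stricture that has already happened. The zero-vs-zero result needs the completer rule in 7.3 as well, and 7.3 may be relaxed. The stricture and dysphagia endpoints are secondary, without stated power, in a 20-patient feasibility study.

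Most of this stands, and it limits the size of the problem. A reader might infer that every patient reaching a secondary endpoint must be withdrawn and that the stricture and dysphagia comparisons are emptied of events. The documents do not support that. Mandatory withdrawal is one side of an internal conflict, and dysphagia is analysed through pre- and post-treatment scores (7.2), so the likely damage there is some missing follow-up scores.

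The objection does not remove the conflict. Section 4.4.1 is the only passage headed as the withdrawal rule, its wording is unrestricted, and an attempted call cannot replace endoscopic data.

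**Conclusion.** The concern holds as an unresolved conflict between 4.4.1 and sections 3.1, 3.3 and 6.3, made worse by 7.3. If a site follows 4.4.1 literally, Visit 3 data are lost according to outcome.

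For stricture, the observed difference can shrink anywhere from not at all to completely: 20, about 12 or 0 points at an assumed 30% vs 10%, with none, half or all of the stricture patients dropped. The dysphagia and scarring comparisons can shrink for the same reason, but the documents give no figures from which to size that. All of this rests on assumed rates, on how sites read 4.4.1, and on how strictly 7.3 is applied.

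A reader might also infer that the primary comparison is pulled toward no difference. The arithmetic does not bear this out: with the same assumption applied to both arms, the planned 60-point lift difference becomes anything from 48.9 to 63.9 points over the range shown. For lift the damage is lower precision, without a clear direction of bias.

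**What to change.** Amend three places so that they agree with 3.1, 3.3 and 6.3.

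- **4.4.1:** state whether the endpoint events (stricture, dysphagia, dilation) count as adverse events for withdrawal. Which clinical rule applies is for the investigators to decide; the passages must give one answer.
- **4.4.2:** state that, whatever the withdrawal status, the questionnaires, images and lift grade are recorded whenever the standard-of-care follow-up endoscopy takes place, including an early symptomatic return, and the endoscopist judges it appropriate. The telephone call is used only when no visit occurs.
- **7.3:** state which population the secondary endpoints use, and that strictures recorded before withdrawal count in the secondary analysis.

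The cost is a short amendment and a few extra data items at an endoscopy that is already standard of care. It should be made before enrolment proceeds, because lift grades and images not taken at the time cannot be recovered.
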